We expect a screen fail rate of $\geq 66\%$, thus we anticipate screening roughly 3 or more persons by BP measurements and focused history to find one eligible participant for laboratory screening. From our previous epidemiological work with a population of similar age, we estimate that 30% of adults, 18-40 years of age, will have hyperuricemia as defined by a level of ≥ 6.8 mg/dL.⁷³ Since this information was obtained in 1986, and the trends for obesity and other conditions known to elevate serum urate have increased, it is likely that over 50% of the population of men and women will have serum urate levels ≥ 5.0 and ≥ 4.0 mg/dL, respectively. Also, based on NHANES 1999-2006 data, 53% of men and women age 20 to 35 years with pre-hypertension or stage 1 hypertension have serum urate ≥ 5.0 mg/dL (≥ 4.0 mg/dL for women). When considering this and the past experience of the UAB Hypertension group in screening, we anticipate that about 50% of the laboratory-

screened subjects will be ineligible. In conclusion, we will need to perform screening laboratory assessments in 236 individuals. We have carefully accounted for these recruitment challenges in our study design and budget and anticipate enrolling 30 individuals per year.

Table 1. Enrollment criteria.
Inclusion criteria
Pre-hypertension or stage I hypertension, defined as the following after the mean of two clinic measurements: -Systolic blood pressure (SBP) \geq 120 and $<$ 160 or; -Diastolic blood pressure (DBP) \geq 80 and $<$ 100
Serum urate \geq 5.0 mg/dL for men or \geq 4.0 mg/dL for women
Age 18-40*
Exclusion criteria
Any current pharmacological treatment for hypertension, including diuretics**
Estimated glomerular filtration rate $<$ 60 mL/min/1.73m ²
Current use of any urate-lowering therapy or statins
Prior diagnosis of gout or past use of urate-lowering therapy for gout
Prior diagnosis of diabetes
Pregnancy, or recent delivery or last trimester pregnancy loss more recent than 3 months
Active smokers
Immune-suppressed individuals including transplant recipients or current use of azathioprine.
Leucopenia with absolute white cell count $<$ 3000 /mL, anemia with hemoglobin $<$ 12 g/dL, or thrombocytopenia with platelet count $<$ 150,000/mL
Abnormal liver function tests (AST $>$ 40 Units/L, ALT $>$ 58 Units/L, Alkaline Phosphatase $>$ 117 Units/L)
Individuals of Han Chinese or Thai descent with HLAB5801 genetic phenotype

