Allopurinol hypersensitivity syndrome (AHS) is a very rare (occurs in less than 1 in 1000 patients), life threatening idiosyncratic reaction that is commonly preceded by rash. published prior report mentions a crude incidence rate of .69 per 1000 person years for severe AHS cutaneous reactions.⁸³ It should be noted that during the course of this study we will expose to allopurinol a total 112 (<30 participants/year) ambulatory young adults aged 18-40, with normal kidney function. The rate of AHS in younger ambulatory patients with normal kidney function has not been established but is possibly lower than in individuals with gout and other medical comorbidities. Allopurinol hypersensitivity syndrome has principally been observed in individuals that are HLAB5801 positive (primarily individuals of Han Chinese or Thai descent). As recommended in the recently released American College of Rheumatology guidelines, we will test for HLAB5801 during initial screening in individuals of Han Chinese or Thai descent.⁸⁴

5.Hypertension

Participants might be exposed to elevated blood pressure during a short period of the study. Given that adverse outcomes associated with hypertension tend to occur over time-periods measured in years and our study extends over a period of only 3-4 months, the risk of short exposure to elevated blood pressure leading to an adverse outcome is small.

To maximize the safety of the participants we have added a safety monitoring rule. When patients are seen at visits 2-5, if present with high blood pressure >160/110, first it will be rechecked 24 hrs later, if blood pressure

is still elevated, they will be excluded from the study, receive consultation by PI and/or Co-PI, and be referred to their primary care provider.

6. Hyperuricemia

Participants will not be treated for asymptomatic hyperuricemia outside the study protocol, given that they are understood not to have been diagnosed with gout for enrollment in the study.

7. Pregnancy

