During the screening phase, potential participants will be determined as described in the Recruitment Plan in section 5A. Study personnel following instructions outlined in the study binder will carry out screenings. The set of screening questions will be asked prior to starting any study procedures and immediately after obtaining consent. These questions will be based on eligibility and exclusion criteria described below (see Appendix 2 for REDCap screenshots). Screening logs will be kept in electronic format and saved in a password protected file folder in the REDCap system (See Appendix 2 for REDCap screenshots) and updated as needed during recruitment.

7. Criteria

7a. Eligibility criteria

A screening visit will occur to confirm study eligibility, explain procedures, and sign an informed consent for screening. For men and women in days 1-7 of the menstrual cycle eligible for the study, randomization and the baseline visit will occur 2 weeks after the screening procedures and signing of the consent form. Women after day 7 of the menstrual cycle will be invited to return after the onset of their menses and no later than day 7 of the next cycle for standardized measurements of FMD (4 week placebo run-in ± 3 days) in the UAB Hypertension Clinic.^{85,84} Participants will be randomized following confirmation of eligibility. We anticipate an additional 10% that initially fulfill inclusion criteria will fail to randomize because their BP will be outside the study range at visit 1. In conclusion, we project the need to perform screening laboratory assessments in 236 individuals. Enrollment and participant follow-up will continue until 112 participants are enrolled. We anticipate recruiting 30 persons per year based on the following inclusion criteria.

1. Pre-hypertension or stage I hypertension, defined as the following after the mean of two clinic measurements:
 - -Systolic blood pressure (SBP) ≥ 120 and < 160 or;
 - -Diastolic blood pressure (DBP) ≥ 80 and < 100
2. Serum urate ≥ 5.0 mg/dL for men or ≥ 4.0 mg/dL for women
3. Age 18-40

7b. Exclusion criteria

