A database will be designed for the current study in the REDCap system. These computerized templates, are accessible through a secure web interface. Data entered into the system will be downloaded weekly and the database will have range and validity checks built in. All abnormal values will be flagged for further investigation. Research staff performing data entry will be trained in the use of the REDCap system and the study database. The study statistician will develop validity checks for outlier values, consistency, and completeness and will notify the principal investigator if issues are identified. Discrepancies will be adjudicated by consultation with the principal investigators. Once data entry is complete, the study data will be transferred to SAS statistical software and reviewed by the statistician.

16. Safety Monitoring and Reporting

The following defines the types of adverse events that study staff should inquire about at each visit. The type and possible causes of the adverse event will be discussed with the principal investigator, an examination will be conducted if deemed necessary, and it will be reported to the required parties. It is the responsibility of each and every study staff member to determine the appropriate line of action, to take the action agreed upon with the participant, and to subsequently report the event.

- Adverse Event (AE) - An AE is any unfavorable and unintended diagnosis, sign (including an abnormal laboratory finding), symptom, or disease temporarily associated with the study intervention, which may or may not be related to the intervention. AEs include any new events not present during the pre-intervention period or events that were present during the pre-intervention period which have increased in severity.

- Serious Adverse Event (SAE) - An SAE is any untoward medical occurrence that results is life-threatening, requires or prolongs hospitalization, causes persistent or significant disability/incapacity, results in congenital anomalies/birth defects, in death, or, in the opinion of the investigators, represents other significant hazards or potentially serious harm to research participants or others. All SAEs will be reported to the Safety officer (via KAI), Data Safety and Monitoring Board (DSMB), and IRB within 48 hours of the Principal Investigator becoming aware of the event.
- *Unexpected adverse event: Any adverse event, the specificity, frequency or severity of which is not consistent with either:*

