control and to compare its effects to placebo in 112 participants with prehypertension and stage I hypertension. [REDACTED] will be responsible for data safety and monitoring. As PIs they will complete and submit to the Project Advisory Committee monthly reports detailing the study progress and participant status, any adverse events, and any protocol deviations. Continuous, close monitoring of individual participant by the PIs will be assured throughout the study period. Events determined by the PIs to be serious, unanticipated problems involving risks, those not described in **Table 8. Adverse Events**, to the participants will be reported by the PIs to the IRB, DSMB, and the Safety Officer (via KAI) within 48 hours.

Table 8. Adverse Events – This document will be updated as needed.

Activities of Daily Living-ADL

Body Surface Area- BSA

Body System			
Cardiovascular	Mild	Moderate	Serious
Myocardial Infarction			All reported myocardial infarction will be classified as serious
Increased Blood Pressure	Systolic BP 140 - 159 mm Hg or diastolic BP 90 - 99 mm Hg; medical intervention indicated	Systolic BP \geq 160 mm Hg or diastolic BP \geq 100 mm Hg; medical intervention indicated	Life-threatening consequences (e.g., malignant hypertension, transient or permanent neurologic deficit, hypertensive crisis)
Hematology	Mild	Moderate	Serious
Anemia	13-10 Hb g/dl)	10-8 Hb g/dl	<8 Hb g/dl
Thrombocytopenia	150 000- 75 000/mm ³	<75,000 – 50,000/mm ³	<50,000 – 25,000/mm ³
Neutropenia	<LLN – 1500/mm ³	<1500-1000/mm ³	<1000-500/mm ³
Gastrointestinal	Mild	Moderate	Serious
Vomiting	1 - 2 episodes (separated by 5 minutes) in 24 hrs	3 - 5 episodes (separated by 5 minutes) in 24 hrs	\geq 6 episodes (separated by 5 minutes) in 24 hrs; tube feeding, TPN or hospitalization indicated
Diarrhea	Increase of <4 stools per day over baseline; mild increase in ostomy output compared to normal	Increase of 4 - 6 stools per day over baseline; moderate increase in ostomy output compared to normal	Increase of \geq 7 stools per day over baseline; incontinence; hospitalization indicated; serious increase in ostomy

Project 2: The Effects of Urate Lowering Therapy on Inflammation, Endothelial Function, and Blood Pressure (NIAMS: CORT)

			output compared to normal or death

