Abdomen	 Normal  Abnormal reset
Heart / Lung	 Normal  Abnormal reset
Neuro	 Normal  Abnormal reset
Family Medical History	
Gout	 Yes  No reset
Comments	
Hypertension	 Yes  No reset
Angina/Myocardial Infarction	 Yes  No reset
Stroke	 Yes  No reset
Diabetes	 Yes  No reset
Other	 Yes  No reset
Sample Collection	
Blood sample drawn (Red top, purple top, green top)	 Yes  No reset
Urine sample collected?	 Yes  No reset
Pill Distribution	
Patient eligible for 2-week run-in period?	 Yes  No reset
Pill bottle serial number	
Number of pills given	
REMINDER: Go to scheduling page/calendar to schedule/confirm date of appointment	

Screenshot 5. Screening visit #3 – Laboratory results

Event Name: SCREEN: Visit	
Record ID Field	888
Medical Record Number	
Pregnancy test	 Negative  Positive reset
Cotinine test	 Negative  Positive reset
Alkaline Phosphatase (39-117 Units/L)	
AST (14-40 Units/L)	
ALT (10-44 Units/L)	
Hemoglobin (12-15 g/dL)	
WBC (4000-11,000)	
Platelet count (150,000-400,000)	
Serum Uric Acid (2.0-6.9 mg/dl)	
Serum Creatinine (0.4-1.2 mg/dL)	
Estimated Glomerular filtration rate (ml/min)	 View equation
NOT ELIGIBLE TO CONTINUE	

Appendix 2

Screenshot 6. Phone Check-in #1

Event Name: SCREEN: Phone check-in A	
Record ID Field	888
Enrollment confirmed	 Yes  No reset
Menstrual cycle information	
Date of Visit 1	  Y-M-D YYYY-MM-DD
Form Status	
Complete?	
 	

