1st measure - DBP (mm Hg)	
Blood Pressure 2	
Time - 2nd Blood Pressure measurement	  H:M
BP2 - Sitting pulse	
2nd measure - SBP (mm Hg)	
2nd measure - DBP (mm Hg)	
Blood Pressure 3	
Time - 3rd Blood Pressure measurement	  H:M
BP3 - Sitting pulse	
3rd measure - SBP (mm Hg)	
3rd measure - DBP (mm Hg)	
Mean SBP	 View equation
Mean DBP	 View equation

Screenshot 11. Visit 2-5 #3 – Sample collection and laboratory results

Record ID Field	888
VISIT LABS	
Blood drawn (red top, 2 purple tops, green top, SST)	 Yes  No
Blood draw - time	
Sample Tube ID	
Sent to Lab	 Yes  No
Sent to Lab - time	
Urine collected	 Yes  No
Urine collection - time	
Sample Tube ID	
Sent to Lab	 Yes  No
Sent to Lab - time	
Sample sent for serum banking (purple top, SST)	 Yes  No
Serum bank - time	
Pregnancy test	 Negative  Positive
Continine test	 Negative  Positive
Scheduled Date (from calendar)	 Today Y-M-D <small>YYYY-MM-DD</small>
Lab Results	
Alkaline Phosphatase (39-117 Units/L)	
AST (14-40 Units/L)	
ALT (10-44 Units/L)	
Hemoglobin (12-15 g/dL)	
WBC (4000-11,000)	
Platelet count (150,000-400,000)	
Serum Uric Acid (2.0-6.9 mg/dl)	
Serum Creatinine (0.4-1.2 mg/dL)	
Estimated Glomerular filtration rate (ml/min)	 View equation
Highly Sensitive C-Reactive Protein (mg/L)	

Screenshot 12. Visit 2-5 #4 – Flow-mediated dilation

Record ID Field	888
FLOW-MEDIATED DILATION (FMD)	
Performed by	
Assistant	
Start time	
End Time	

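### Table 8 starts mild anemia inside the eligible and form-normal hemoglobin range, and grades neutropenia on a neutrophil count that the laboratory forms do not record

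*Combined protocol and SAP*

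**What the plan says.** **AE definition (section 16).** An AE is an unfavorable sign, and for laboratory data the text speaks of an abnormal finding. It must be new since the pre-intervention period, or be among "events that were present during the pre-intervention period which have increased in severity".

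**Anemia (Table 8).** The mild band is Hb 13-10 g/dL, moderate 10-8, serious below 8. The table gives no split by sex. Table 1 excludes "anemia with hemoglobin $<$ 12 g/dL, or thrombocytopenia with platelet count $<$ 150,000/mL". The screening and Visit 2-5 laboratory forms (Appendix 2, Screenshots 5 and 11) both print "Hemoglobin (12-15 g/dL" as the range.

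**Neutropenia (Table 8).** Mild runs from the LLN to 1,500/mm³, moderate from 1,500 to 1,000, serious from 1,000 to 500. The only white-cell field on the same two forms is "WBC (4000-11,000", a total count. The AE form (Screenshot 14) has a neutropenia entry. A complete blood count (CBC) is scheduled at Visits 1-5 (Table 3). Section I.4 names bone marrow suppression among the allopurinol risks that may not be reversible.

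**Blood pressure (Table 8).** The mild cell reads "Systolic BP 140 - 159 mm Hg or diastolic BP 90 - 99 mm Hg; medical intervention indicated". The moderate cell starts at systolic 160 or diastolic 100 and repeats the phrase: "100 mm Hg; medical intervention indicated". Entry (section 7a) allows systolic 120 to below 160, or "Diastolic blood pressure (DBP) ≥ 80 and < 100". The on-study rule in section I.5 applies at Visits 2-5: "if present with high blood pressure >160/110, first it will be rechecked 24 hrs later".

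**Use of the grades.** Table 7 lists an AE summary by body system and severity. Section 16 sends AE tables to the Safety Officer every 12 weeks.

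**The concern.** A severity scale works when its mildest grade begins where a value stops being normal and when its grades can be read from recorded data. The anemia row fails the first test and the neutropenia row fails the second.

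For anemia, a participant whose Hb goes from 13.2 to 12.8 has crossed into a Table 8 grade without leaving the range on the form. One coder may record mild anemia because Table 8 says so. Another may record nothing because the value is not abnormal. The text does not settle which is right.

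For neutropenia, staff are asked for a grade, and for a judgment of worsening since baseline, without a recorded count or a printed LLN. What is at stake is the consistency and meaning of two rows of the safety tables, one of which concerns a recognized hazard of the study drug.

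**Working it through.** The plan gives no figure to reproduce here, so the check compares its thresholds.

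**1. Hemoglobin overlap**
- Mild band: 10 to 13 (Table 8).
- Eligible: 12 or above (Table 1).
- Form range: 12 to 15 (Screenshots 5 and 11).
- Intersection of all three: 12 to 13 g/dL. That is (13 - 12)/(15 - 12) = 1/3 of the form range and (13 - 12)/(13 - 10) = 1/3 of the mild band.

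Other rows begin where the form's range ends. Mild thrombocytopenia starts at 150,000, which is both the entry limit and the form's lower limit. Mild liver-enzyme elevation starts above the upper limit of normal. Mild neutropenia is set at the LLN. Anemia alone starts inside the range.

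**2. How often Hb could cross 13 with no drug effect (illustration only)**

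The documents give no Hb distribution. Assume a usual value m and independent normal visit-to-visit variation with SD s of 0.3 or 0.5. A new event needs both pre-drug values (Visits 1 and 2) at 13 or above and at least one of Visits 3-5 below 13. With q = 1 - Φ((13 - m)/s), the chance is q² × (1 - q³).

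| m | s | q | q² | 1 - q³ | chance |
|---|---|---|---|---|---|
| 13.2 | 0.3 | 0.748 | 0.559 | 0.582 | 33% |
| 13.2 | 0.5 | 0.655 | 0.430 | 0.718 | 31% |
| 13.5 | 0.3 | 0.952 | 0.907 | 0.137 | 12% |
| 13.5 | 0.5 | 0.841 | 0.708 | 0.404 | 29% |
| 14.0 | 0.3 | 0.9996 | 0.999 | 0.001 | 0.1% |
| 14.0 | 0.5 | 0.977 | 0.955 | 0.067 | 6% |

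At m = 13.2 the last factor alone, 58-72%, overstates the matter: it includes people already below 13 before drug, for whom the finding is not new. Nor would a cut-off of 12 abolish such crossings; someone with a usual Hb of 12.2 would cross it equally often. The difference is that a value below 12 is outside the form's range and a value of 12.8 is not.

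**3. Neutrophils from total white cells**

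The count is total white cells (WBC) × neutrophil share. It is below 1,500, Table 8 moderate, when the share is under 1,500/WBC. I take the form's count and the entry limit of 3,000 as per mm³.
- WBC 3,000 (lowest eligible): 1,500/3,000 = 50%.
- WBC 4,000 (form's lower limit): 1,500/4,000 = 37.5%.
- WBC 5,000: 1,500/5,000 = 30%.

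For an assumed share of 30-70%, WBC 4,000 means 1,200 to 2,800 neutrophils. That spans the moderate grade and values above 1,500, where the grade turns on an LLN that is not printed. The recorded field puts a ceiling on the neutrophil count but does not determine the grade.

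**4. Blood pressure wording**
- Systolic 140-159 is the upper 20 of the 40 mmHg entry range.
- Diastolic 90-99 is the upper 10 of the 20 mmHg entry range.
- A reading of 142/88 is admissible at entry, falls in the mild cell with its intervention phrase, and does not trigger the rule above 160/110.
- Where other mild cells mention intervention (other gastrointestinal, nervous, itch), they say that none is called for.

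**The case against.** **Severity is not the same as being an AE.** Section 16 decides what counts as an AE, and an Hb of 12.5 on a 12-15 range need not be abnormal. This is the best answer on anemia, and it does dispose of stable entry values: a reader might infer that anyone entering with Hb 12.5 or pressure 150/95 starts the trial with an AE, and the definition rules that out. It does not settle a new fall to 12-13, because Table 8 itself labels that value mild anemia.

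**The anemia cell may be incomplete.** It ends in a closing parenthesis with no opening one, so a typing slip or lost text is possible, and 13 may have been meant as a male limit. That should be checked against the source. With recruitment aimed at equal numbers of men and women, a sex limit would have to be stated.

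**Table 8 does not follow entry limits.** True: entry allows ALT up to 58 while the form's upper limit is 44. But the liver row does follow the laboratory limit, and that is the standard the anemia row misses.

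**A CBC is drawn and reviewed.** Section L.2 has the principal investigator or a co-investigator review blinded laboratory data, section 15b flags abnormal values, and the laboratory may hold a differential. A reader might infer that marrow suppression would go unseen; the documents do not support that. What stands is that neither the count nor its LLN has a field on the forms.

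**Blood pressure.** A reader might infer that Table 8 contradicts the rule above 160/110, or that a diastolic of 100-110 is left without a response. Neither follows. A severity grade and a withdrawal limit may differ, Table 8 says it derives from a standard grading scale, and section 16 and Appendix 3 (E.3) leave AE treatment to the investigator. Only the wording of the mild cell remains open to criticism.

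**Conclusion.** Two defects hold on the printed thresholds alone. The mild anemia band overlaps the eligible and form-normal range by 1 g/dL, and the neutropenia grades cannot be derived from the recorded laboratory fields. The Hb frequencies rest on assumed usual values and variation: 31-33% for a usual value of 13.2, falling to 0.1-6% at 14.0. They show that the overlap could matter for people near 13, not how many such people will be enrolled. The neutrophil point assumes that the forms shown hold all the white-cell data recorded; the documents do not say whether a differential is reported.

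The intervention phrase in the mild blood pressure cell is a minor wording matter. A reader might also want a minimum change in pressure before an AE is counted, a separate action rule for diastolic 100-110, or a renal row. The documents give no basis for a particular minimum change, and none of these is needed to repair the two defects.

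The effect is confined to consistent grading and readable safety tables. The stopping rule in section K counts severe cutaneous reactions, and no efficacy analysis uses these grades. The changes should be made, but the trial's conclusions do not hang on them.

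**What to change.** 1. **Anemia.** Start the mild grade at the laboratory's lower reference limit: 12 as the form stands, or sex-specific limits if the laboratory uses them, printed on the form and in Table 8.
2. **Neutropenia.** Add an absolute neutrophil count, with its LLN, to the screening and Visit 2-5 laboratory forms.
3. **Blood pressure.** Delete the intervention phrase from the mild cell.

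The plan already expects Table 8 to be revised as needed, and the CBC is drawn at every visit, so no extra blood is taken. The costs are the form change, a possible request to the laboratory for the differential, and recoding any AEs already graded under the present rows.
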